5.6 Drug Administration

5.6.1 Treatment Assignments

The first three patients will be treated at dose level 1. Subsequent increases in dose level will occur as outlined under 5.1. after approval by the PI.

5.6.2 Dosing Regimen

The trial will use a classical 3x3 phase I design for patients with GFR > 60ml/min and a modified 3x3 design for patients with GFR 30-59ml/min with enrollment of ten additional patients at the highest tolerated low dose (HTLD / HTLD-CKD) of azacitidine as outlined under 5.1. The dosing schedule is outlined below. Assigned combination treatment with lenalidomide, azacitidine, and dexamethasone will be continued for six 28-day cycles followed by maintenance treatment with lenalidomide single agent at the last tolerated dose until disease progression with adjustment of dose as outlined under 5.7.1 and 5.7.3.

Peripheral blood stem cell harvesting and high dose chemotherapy therapy may be performed at any point after treatment cycle #2. In such patients protocol therapy will be permanently discontinued at least five days before stem cell mobilization begins but in addition to the basic follow up outlined under 2, schedule of study assessments, their peripheral blood stem cell yield and engraftment will be documented.

5.6.2.1 Special Handling Instructions

Females of childbearing potential should not handle or administer lenalidomide and azacitidine unless they are wearing gloves.

5.6.2.2 Record of administration

Accurate records will be kept in the source documents of all drug administration (including prescribing and dosing).

5.6.2.3 Combination Therapy

Dosing Schedule for Patients with GFR \geq 60ml/min (Cockroft-Gault)

Dose level	Azacitidine (s.c.)* Starting day 1	Lenalidomide (p.o.) Starting day 1	Dexamethasone (p.o.)
------------	---------------------------------------	---------------------------------------	----------------------

1	30mg/m ² once a week ¹	25mg d1-21 every 28d ³	40mg p.o. once a week ⁴
2	40mg/m ² once a week ¹	25mg d1-21 every 28d ³	40mg p.o. once a week ⁴
3	30mg/m ² s.c. twice a week ²	25mg d1-21 every 28d ³	40mg p.o. once a week ⁴
4	40mg/m ² s.c. twice a week ²	25mg d1-21 every 28d ³	40mg p.o. once a week ⁴
5	50mg/m ² s.c. twice a week ²	25mg d1-21 every 28d ³	40mg p.o. once a week ⁴

* After highest tolerated low dose (HTLD) of azacitidine determination, azacitidine starting dose will be at the HTLD

Dosing Schedule for Patients with GFR 30-59ml/min (Cockcroft-Gault)

Dose level	Azacitidine (s.c.)* Starting day 1	Lenalidomide (p.o.) Starting day 1	Dexamethasone (p.o.)
-1	30mg/m ² s.c. twice a week ²	10mg d1-21 every 28d ³	40mg p.o. once a week ⁴
1	40mg/m ² s.c. twice a week ²	10mg d1-21 every 28d ³	40mg p.o. once a week ⁴
2	50mg/m ² s.c. twice a week ²	10mg d1-21 every 28d ³	40mg p.o. once a week ⁴

* After highest tolerated low dose (HTLD-CKD) of azacitidine determination, azacitidine starting dose will be at the HTLD-CKD

¹ Ideally, azacitidine is administered on the same day each week, but +/- up to two days is allowed, individual doses should be at least 5 days apart. Rotation of injection sites is obligatory.

² Azacitidine should be administered on the same days each week, +/- one day is allowed but there should be at least 48hrs between doses. The following schedules are recommended: Monday-Thursday, Monday-Friday, Tuesday-Friday, Tuesday-Saturday. Rotation of injection sites is obligatory

³: Lenalidomide dosing will be in the evening at approximately the same time each day. Prescriptions must be filled within 7 days. If a dose of lenalidomide is missed, it should be taken as soon as possible on the same day. If it is missed for the entire day, it should not be made up. Patients who take more than the prescribed dose of lenalidomide should be instructed to seek emergency medical care if needed and contact study staff immediately.

⁴: Dexamethasone dosing, independent of age, will be in the morning with breakfast. Dexamethasone should be taken at least 24h after and not less than 24h before azacitidine to maximize the s-phase specific epigenetic effects of azacitidine.

5.6.2.4 Lenalidomide Maintenance Treatment and Guidelines for Re-Introduction of Azacitidine and Dexamethasone

After six 28-day cycles on combination therapy, dexamethasone and azacitidine will be discontinued and lenalidomide will be continued as a single agent at the last tolerated dose until disease progression. At physician discretion, for patients with response < PR after six 28-day cycles on combination therapy, the dose of lenalidomide may be

escalated during maintenance treatment to a maximum dose of 25mg daily on Days 1-21 of each 28-day cycle. Lenalidomide dose titration may only occur at the start of a new cycle of maintenance one dose level at a time, and only in patients who completed the previous treatment cycle without dose modifications or treatment delays due to toxicity. Lenalidomide dose titration may occur NOT more frequently than once every 28 days. After 12 months since initiation of protocol therapy, no further lenalidomide dose titration is permitted. Also for patients with response < PR after six 28-day cycles on combination therapy, dexamethasone and/or azacitidine may be continued or restarted (if it had been discontinued) at physician discretion. In particular, patients with response < PR after six 28-day cycles on combination therapy that have not shown sufficient signs of end organ improvement should be considered for lenalidomide dose titration and/or additional dexamethasone and/or azacitidine as outlined above. Similarly, patients who have achieved disease control (stable disease or better) during the first six 28-day cycles of combination therapy and who's myeloma progresses on maintenance therapy may be restarted on lenalidomide, azacitidine, and dexamethasone combination therapy at the last tolerated dose at physician discretion.

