If the patient's GFR increases from 30-59ml/min at enrollment to ≥ 60 ml/min at the start of a cycle and the previous cycle was tolerated without need for dose reduction of lenalidomide due to any adverse event and no G-CSF or platelet transfusions were required, the dose of lenalidomide may be increased by one dose level according to table 2. If the dose of lenalidomide or azacitidine was reduced due to renal impairment on study, and continued treatment results in calculated creatinine clearance ≥ 60 ml/min (by Cockcroft-Gault), the dose of lenalidomide and azacitidine can be increased by one dose level each at the start of each cycle until the target dose of both drugs is reached provided the calculated creatinine clearance remains ≥ 60 ml/min (by Cockcroft-Gault) and no relationship between study drugs and renal impairment was suspected. If a relationship between study drugs and renal impairment is considered possible, drug increases should be done one drug at a time and alternating between lenalidomide and azacitidine, starting with lenalidomide. Doses may be increased only in patients who completed the previous treatment cycle without dose modifications or treatment delays due to toxicity (regardless of type). Dose increases may occur NOT more frequently than once every 28 days. If the current dose of lenalidomide is 15 mg every 48 hours during Days 1-21 every 28 days, or 5 mg daily on Days 1-21 every 28 days, the first dose increase would be to 10 mg daily on Days 1-21 every 28 days. Additional dose increases if warranted would be in 5 mg increments. After 12 months since initiation of protocol therapy, no further lenalidomide dose titration is permitted.

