5.7.4 Instructions for Initiation of a New Cycle

A new course of treatment may begin on the scheduled Day 1 of a new cycle if:

- The ANC is $\geq 1000/\text{mm}^3$ (G-CSF is allowed to achieve this threshold)
- The platelet count is $\geq 50,000/\text{mm}^3$ (During the first 4 cycles platelet transfusions are allowed to achieve this threshold)
- Any new drug-related neuropathy or rash other than injection site reaction that may have occurred has resolved to \leq grade 1 severity;
- Any bicarbonate decrease below 20mEq/L that may have occurred has resolved to baseline.
- Calculated creatinine clearance $\geq 30\text{ml}/\text{min}$ (by Cockroft-Gault), after 12 cycles on therapy, determining the creatinine clearance every 2 months will suffice
- Any other drug-related adverse events that may have occurred have resolved to \leq grade 2 severity. Physician discretion may be used in initiating the next cycle of treatment if the only toxicities that have not resolved to \leq grade 2 severity are dexamethasone-related toxicities.

If these conditions are not met on Day 1 of a new cycle, the subject will be evaluated weekly and a new cycle of treatment will not be initiated until the toxicity has resolved as described above. If criteria to initiate a new cycle are not met by 21 days after the planned start of a new cycle patients go off study. If a lenalidomide or azacitidine dose reduction was taken during the previous cycle, and the cycle was completed without requiring further dose modification, then the next cycle will start at the same reduced dose. **If lenalidomide and / or azacitidine dosing was omitted for the remainder of the previous cycle or if the new cycle is delayed due to toxicity newly encountered on the scheduled Day 1**, then the new cycle will be started with a one-level dose reduction of lenalidomide and/or azacitidine as appropriate. Dose reductions should generally be taken one drug at a time based on attribution of toxicity to one of the drugs unless otherwise indicated in Section 5.7.3.

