Venous thrombosis/embolism \geq Grade 3	
 Hold (interrupt) lenalidomide and start anticoagulation; restart lenalidomide at investigator's discretion (maintain dose level). Omit lenalidomide for remainder of cycle. See Anticoagulation (Section 5.8.1.2)
Hyperthyroidism or hypothyroidism	
 Omit lenalidomide for remainder of cycle, evaluate etiology, and initiate appropriate therapy. See Instructions for Initiation of a New Cycle and reduce the dose of lenalidomide by 1 lenalidomide dose level.
Bicarbonate - low (CO₂ below 20mEq/L)	
 If unexplained hold azacitidine and lenalidomide Check weekly Upon recovery to baseline restart azacitidine at next lower dose level and restart lenalidomide at the current dose. If recovery to baseline occurs prior to Day 21 of the current cycle, restart as instructed above and continue treatment through the scheduled end of the cycle. Otherwise, omit treatment for remainder of cycle and reduce the dose of azacitidine by 1 dose level and maintain the current dose of lenalidomide at the start of the next cycle. Omitted doses are not made up.

Table 5: Dose Modifications Azacitidine and Lenalidomide

NCI CTC Toxicity Grade	Dose Modification Instructions
Renal impairment (Calculated creatinine clearance \geq 30ml/min < 60ml/min)	
 Maintain current dosing schedule, but reduce lenalidomide by 1 dose level (see Section 5.7.1, Table 2). If lenalidomide dose had been \geq 15mg, reduce to 10mg daily on Days 1-21 of each 28-day cycle.

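### Section 5.6.2.4 lets maintenance lenalidomide rise to 25 mg with no creatinine clearance condition, out of line with the protocol's renal dosing rules at clearance 30-59 ml/min

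*Combined protocol and SAP*

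**What the plan says.** Section 5.6.2.4 governs lenalidomide after six cycles of combination therapy. If response is below PR, the dose may be "escalated during maintenance treatment to a maximum dose of 25mg daily on Days 1-21 of each 28-day cycle". The conditions are:

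- response below PR;
- physician discretion;
- start of a maintenance cycle;
- one dose level at a time;
- a previous cycle completed "without dose modifications or treatment delays due to toxicity";
- no more than one change per 28 days;
- no titration after 12 months.

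Renal dosing is set elsewhere:

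- **5.6.2.3** assigns every dose level of the GFR 30-59 cohort lenalidomide "10mg d1-21 every 28d". The synopsis calls this a fixed dose. Exclusion criterion 9 treats 10 mg as full dose at clearance 30 to below 60.
- **5.7.3** covers a patient enrolled at 30-59 whose GFR reaches 60 or more at a cycle start: "the dose of lenalidomide may be increased by one dose level according to table 2". For patients being stepped back up from the lowest renal doses, it adds: "Additional dose increases if warranted would be in 5 mg increments".
- **5.7.5, Table 5**, has a row for clearance from 30 to below 60. It reduces lenalidomide by one level and, if the dose had been 15 mg or more, says to "reduce to 10mg daily on Days 1-21 of each 28-day cycle".
- **5.7.4** lets a new cycle start at clearance of 30 or more. After 12 cycles, "determining the creatinine clearance every 2 months will suffice".
- **5.6.2** says that maintenance continues at the last tolerated dose "with adjustment of dose as outlined under 5.7.1 and 5.7.3".

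**The concern.** A patient enrolled at 30-59, stable on 10 mg and below PR after six cycles, can meet every condition in 5.6.2.4. The cycle-start check in 5.7.4 does not stop the increase, because it asks only for clearance of 30. A physician could therefore raise lenalidomide above the protocol's own renal dose and stay within the wording of 5.6.2.4, while other sections point back to 10 mg.

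The stake is dosing safety in maintenance. Three features of the text add to it:

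- 5.6.2.4 says that patients without enough end-organ improvement should be considered for titration. Rising creatinine attributed to myeloma is one of the clinical criteria in 5.3.2, so the wording can steer titration toward persistent renal impairment.
- Section 4.2.1 moves blood counts from weekly to once per cycle after cycle 6, just as titration opens.
- The same paragraph lets azacitidine be continued or restarted.

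**Working it through.** No sample size, power or alpha figure is involved, and the plan gives no figure of its own to reproduce. The check is a comparison of sections plus simple arithmetic.

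**1. The rules for a patient still at clearance 30-59**

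| Section | Bearing on a rise above 10 mg |
|---|---|
| 5.6.2.4 | Permitted up to 25 mg; clearance not mentioned |
| 5.7.4 | Cycle may start at 30 or more; no bar |
| 5.7.3 | Renal route upward opens at 60 or more; silent on escalation for poor response |
| 5.6.2.3 and exclusion 9 | 10 mg is the assigned and full dose (the 5.6.2.3 table governs combination therapy) |
| Table 5 | 15 mg or more goes back to 10 mg |
| 5.6.2 | Points maintenance adjustment to 5.7.1 and 5.7.3; does not name 5.7.5 |

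The first increase to 15 mg or more already meets the Table 5 trigger. No sentence ranks these rules.

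**2. What one dose level means**

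5.6.2.4 names no table. On Table 1 the level above 10 mg daily is 15 mg, but its title excludes renal impairment. On Table 2 the level above 10 mg daily is 25 mg.

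**3. Whether 25 mg can be reached within 12 months**

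Cycle k starts on day 28(k-1)+1, assuming no delays. Cycle 7 is day 169, cycle 8 day 197, cycle 9 day 225, cycle 10 day 253, cycle 13 day 337 and cycle 14 day 365.

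- Table 1 steps (10-15-20-25): 25 mg at cycle 9 (day 225), or cycle 10 (day 253) if a maintenance cycle must be completed first.
- Table 2 step (10-25): 25 mg at cycle 7 (day 169), or cycle 8 (day 197) on the same condition.

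All four fall inside the limit.

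**4. Exposure, GFR 30-49 only**

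Inputs from 5.1.1.3: in seven patients at GFR 30-49, average daily AUC on 10 mg was 103% of that on 25 mg at GFR above 80. Exposure was dose proportional from 5 to 50 mg in 15 phase I patients. Proportionality in renal impairment is an assumption.

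Relative AUC = 103% x dose/10:

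- 15 mg: 103% x 1.5 = 154.5%
- 20 mg: 103% x 2.0 = 206%
- 25 mg: 103% x 2.5 = 257.5%

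These figures do not carry over to GFR 50-59. There the cited study gave 25 mg (its 50-80 group), and no CKD group averaged above 149%.

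**5. Patients who could be affected**

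The synopsis caps CKD dose finding at 12 patients, and 5.1 lets patients treated at HTLD-CKD count toward the 10-patient extension. The ceiling is 12 + 10 = 22 of 44, before replacements. The documents do not give the number still on treatment, below PR and still at 30-59 after six cycles.

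**The case against.** The best defence is that the renal rules already govern. Section 5.6.2 places maintenance dosing under 5.7.1 and 5.7.3, and 5.7.3 carries the condition of 60 or more. The number 5.7.3 may even be a stale reference to the Table 5 section: 5.1 and 5.7.4 both cite 5.7.3 for dose reductions, yet the current 5.7.3 deals only with re-escalation, and Table 3 cites a 5.7.1.2 whose content now sits in 5.7.2. Table 5 has maintenance instructions, so it does apply after cycle 6. The objectives specify GFR-adjusted lenalidomide. A discretionary permission with a maximum can stand beside a mandatory renal limit, and the patient then receives the lower dose.

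Most of this stands as evidence of intent, and it softens the conflict. It does not close the gap. 5.6.2.4 reads as a separate, response-based permission with its own 25 mg ceiling; 5.7.3 does not address poor response; and nothing says which rule prevails.

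A reader might go further and infer a flat contradiction with Table 5 for everyone enrolled at 30-59. The documents do not support that. The Table 5 row is written as a response to a toxicity on study, and read literally for this cohort it would also cut the assigned 10 mg. Its clear bearing here is the sentence on doses of 15 mg or more. If the row covers only a new decline, there is no Table 5 conflict for this cohort, but then its members have no explicit cap on response-based escalation. Either reading leaves something to repair.

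**Conclusion.** The point holds as a gap between sections: 5.6.2.4 permits escalation above the protocol's renal dose at clearance 30-59, and neither the precedence of the rules nor the size of a step is stated. It should be corrected, although the likely intent is clear.

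The affected number is unknown: at most 22 of 44, which requires all ten extension patients to come from the 30-59 group, and probably far fewer. Patients enrolled at 60 or more whose clearance later falls are largely covered by Table 5 and 5.7.3.

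Two larger inferences are not supported. One is that exposure of about 258% should be expected. That figure needs escalation all the way to 25 mg despite Table 5, proportionality in renal impairment and a mean from seven patients, and it says nothing about GFR 50-59. The other is that the primary endpoint is at risk. DLTs are counted in cycle 1 and titration starts only after cycle 6, so HTLD-CKD is unaffected.

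**What to change.** Add to 5.6.2.4: *Lenalidomide may be titrated above 10 mg daily only if calculated creatinine clearance at that cycle start is 60 ml/min or more; the renal limits in 5.7.3 and Table 5 take precedence over this section.*

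Do not prescribe 5 mg steps in this sentence unless the Table 2 step in 5.7.3 (10 to 25 mg) is amended to match; otherwise the new text would disagree with the section to which it gives precedence. If Table 5 is also reworded to cover only a new decline on study, keep an explicit 10 mg cap for patients enrolled at 30-59.

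The cost is small. Section 2, footnote 4, already requires clearance at each cycle start until cycle 12 and then every two cycles, so only cycle 13 (day 337) might need one extra calculation. The clinical price is less room to escalate at GFR 50-59, where the cited study gave 25 mg.

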5.6.2.5 Anticoagulation

Throughout the study, patients who receive lenalidomide (not while the drug is held for high dose chemotherapy and ASCT), who have none of the following risk factors for VTE will receive aspirin 81-325mg daily. If patients have one or more risk factors as outlined below, more intensive prophylaxis should be considered with enoxaparin, 40mg s.c. daily if their GFR (according to Cockcroft-Gault, Appendix IV) is \geq 30ml/min and 30mg s.c. daily if it is < 30ml/min. Alternatively, full anticoagulation with warfarin to a target INR of 2.0-3.0 may be used if \geq 1 risk factor is present. Enoxaparin or warfarin at above doses may also be used for patients with no risk factor if aspirin is not tolerated.

Risk factors:

- Previous venous thromboembolism
- Central venous catheter
- Cardiac pacemaker
- Chronic kidney disease as defined by a GFR < 30ml/min lasting > 28 days
- Symptomatic coronary artery disease or heart failure with a left ventricular ejection fraction < 30%
- Diabetes mellitus (unless controlled with diet alone)
- Acute infection, necessitating hospitalization
- Immobility with bed rest > 50% of daytime (ECOG PS \geq 3) due to any reason while on study
- General surgery or anesthesia

- Treatment with erythropoiesis stimulating agents
- Hereditary hypercoagulability
- Symptomatic hyperviscosity

Subjects experiencing adverse events may need study treatment modifications (See section 5.7).

5.7 Dose Continuation, Modification and *Interruption*

Subjects will be evaluated for AEs at each visit with the NCI CTCAE v.4.0 (Appendix III: NCI CTCAE v.4.0) used as a guide for the grading of severity. Sections below describe recommended dose reduction steps, instructions for initiation of a new cycle of therapy and dose modifications during a cycle of therapy. Clinical judgment may be used when deciding which drug to hold or modify in scenarios that are not covered below. Patients encountering a dose-limiting toxicity during their first cycle may remain on study with appropriate reduction steps.

5.7.1 Dose Modification Steps and Dose Re-Escalation Guidelines

5.7.1.1 Dose Modification Steps

Table 1: Lenalidomide dose modification steps for all toxicities listed in Table 5 EXCEPT for renal impairment or toxicities in the presence of renal impairment*

Current Lenalidomide Dose	One Level Dose Reduction
25 mg daily on Days 1-21 every 28 days	20 mg daily on Days 1-21 every 28 days
20 mg daily on Days 1-21 every 28 days	15 mg daily on Days 1-21 every 28 days
15 mg daily on Days 1-21 every 28 days	10 mg daily on Days 1-21 every 28 days
10 mg daily on Days 1-21 every 28 days	5 mg daily on Days 1-21 every 28 days
5 mg daily on Days 1-21 every 28 days	Discontinue lenalidomide

* Renal impairment is defined as calculated creatinine clearance \geq 30mL/min but $<$ 60mL/min (see Table 2 below for lenalidomide dosing)

Table 2: Lenalidomide dose modification steps for renal impairment (see Table 5) and for other toxicities which occur after dose reduction for renal impairment*

Current Lenalidomide Dose	One Level Dose Reduction
25 mg daily on Days 1-21 every 28 days	10 mg daily on Days 1-21 every 28 days
10 mg daily on Days 1-21 every 28 days	15 mg every 48 hours during Days 1-21 every 28 days
15 mg every 48 hours during Days 1-21 every 28 days	5 mg daily on Days 1-21 every 28 days
5 mg daily on Days 1-21 every 28 days	Discontinue lenalidomide

* Renal impairment is defined as calculated creatinine clearance $\geq 30\text{mL/min}$ but $< 60\text{mL/min}$

Table 3: Azacitidine Dose Adjustment Steps

Dose Level +2	100 mg/ m^2 SC twice a week (only for patients on twice a week azacitidine who tolerated azacitidine 75mg/ m^2 SC twice a week but did not respond, see under 5.7.1.2)
Dose Level +1	75 mg/ m^2 SC twice a week (only for patients on twice a week azacitidine who tolerated their full azacitidine starting dose but did not respond, see under 5.7.1.2)
Dose Level 0	Starting azacitidine dose (differs depending on cohort during phase I part, see 5.6.2.3)
Dose Level -1	Reduce dose by 50%, maintain frequency of administration
Dose Level -2	Discontinue azacitidine

Table 4: Dexamethasone Dose Reduction Step

Dose Level – 1	Reduce each dexamethasone dose by 50%
Dose Level – 2	Discontinue dexamethasone

